3.2. STUDY DESIGN

- Single centre prospective randomised-controlled trial
- Duration: 2 years

Figure 1 – Study Design Flow Chart

This is a prospective, randomised-controlled trial investigating the effects of using video media to aid the anaesthetic consent process.

3.3. RECRUITMENT

Potential trial participants will be recruited from the general adult population (i.e. males and females aged over 18yrs) presenting to pre-operative orthopaedic surgical clinic within Imperial College Healthcare NHS Trust at St Mary's and Charing Cross Hospitals. Potential participants will be approached by members of the study team that may or may not be part of the primary care team. All potential participants will be invited to take part with the use of a participant information sheet (PIS), approved by a Research Ethics Committee, that describes the study. The participant will have time to read the PIS and to discuss their participation with others outside the research team (e.g. relatives or friends) if they wish. A

member of the research team will then answer any questions, confirm the participant's eligibility and take written informed consent if the participant decides to proceed. Details of all participants approached for the trial and reason(s) for non-participation (e.g. reason for being ineligible or patient refusal) will be documented. Also the non-participant does not need to give a reason for non-participation and if so will be documented as non-participation in the reason(s) for refusal. All data will be anonymised.

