3. RESEARCH PLAN AND METHODOLOGY

3.1. STUDY POPULATION

Study centre(s)

- Imperial College Healthcare NHS Trust

Study sample

- 206 participants

Inclusion criteria

- ≥ 18 years
- Presenting to pre-operative orthopaedic surgical clinic
- Informed consent

[figure not shown]
Exclusion criteria

- Patients <18 years or vulnerable groups
- Inability to communicate in English or language difficulty that requires an interpreter
- Severe vision or hearing loss if lack of other communication channels
- Private patients
- Prisoners
- Patients who reside outside the United Kingdom (home address)
- Opt-out patients on GP register

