3.5. MEASUREMENTS

Following recruitment, baseline demographic data will be collected on each participant, including age, gender, ethnicity and education level.

Health literacy is the degree to which individuals have the capacity to obtain, process, and understand basic health information and services needed to make appropriate health decisions²⁸. Health literacy may be an important confounding factor within this study; therefore, assessing health literacy will be a useful screening tool prior to conducting the study. Prior to randomisation, participants will be asked to complete the Newest Vital Sign-UK questionnaire (*see appendix 11.2*) to assess health literacy.

For measuring the primary outcome, participant satisfaction, the Client Satisfaction Questionnaire (CSQ-8) will be utilised, which measures the most salient items for the satisfaction with services (*see appendix 11.1*). This will be administered for the control group after receiving standard verbal consent, and the intervention group after receiving video assisted consent.

For measuring the secondary outcomes, a knowledge, attitudes and practices (KAP) questionnaire will be utilised (*see appendix 11.3*). As part of the questionnaire, the participant will be offered the choice of anaesthetic technique between GA and RA. This is to evaluate whether the proportions choosing GA or RA differ between control and intervention groups.

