3.5.1. Summary of pre-randomisation actions

Event	Measurement/Action	Means	Timing	Time
Recruit participants	Inform participants	Participant Information Sheet	At time of recruitment	5-10 minutes
Consent participants	Informed written consent	Online consent form	At time of consent	5 minutes
Demographic data collection	Age, gender, ethnicity, education level	Online questionnaire	Once consented	2-3 minutes
Health Literacy Assessment	Newest Vital Sign-UK	Online questionnaire	Once consented	3-5 minutes

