5. ASSESSMENT AND FOLLOW-UP

Baseline demographic data will be collected for all study patients. These will include age, gender, ethnicity and educational level.

Assessment will be carried out using the following tools:

- CSQ-8 satisfaction questionnaire (appendix 12.1)
- Newest Vital Sign (NVS)-UK (appendix 12.2)
- Knowledge, Attitudes and Practice questionnaire (appendix 12.3), based on information contained in the consent process

Each participant, with their consent, will be informed of the outcome of the trial and any subsequent publication. There is no requirement for follow-up after the investigative period.

There is unlikely to be any losses as the participant will undertake the 2 questionnaires and state their theoretical choice of anaesthesia immediately after undergoing either the traditional verbal consent process and/ or the video-assisted consent process. The only possible loss would be if the participants abruptly withdraws consent to participate if called away for clinical or personal reasons.

The end of the trial will be when the trial database is complete and locked for analysis.

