6. STATISTICS AND DATA ANALYSIS

Two hundred and six patients in total will be randomised using an online randomisation tool. <https://www.graphpad.com/quickcalcs/randomize1.cfm>

Patient satisfaction, the primary endpoint measured by CSQ-8, is expected to be approximately 30 in both arms. VAC and SVC will be considered equivalent if the VAC satisfaction score is no more than 1.5 points lower than the SVC score. With 103 subjects in the Control Group (SVC) and 103 subjects in Experimental Group (VAC), there is an 85% chance that the observed difference (SVC-VAC) in satisfaction scores will be significantly less than 1.5 at the 5% level, if the true means are 30 in both groups. The standard deviation has been assumed to be 4.

After the first 50 participants have been entered into the trial a feasibility analysis will be undertaken. Three outcomes of particular interest will be the accrual rate, the proportion accepting their randomisation and the proportion evaluable (completing all questionnaires). With 50 participants it will be possible to estimate the proportions in the latter two groups with 95% confidence intervals of at most $\pm 15\%$. A record will be kept of the number of participants approached and their reasons for declining to enter the study. With 50 participants it should be possible to identify and remedy any minor issues that are impediments to recruitment. It may be necessary to plan to increase accrual if withdrawals or the number of non-evaluable participants is greater than expected.

The primary analysis will be by intention to treat (ITT). It is planned to make comparisons between groups for normally distributed variables with independent samples t-test or ANOVA, variables that are not normally distributed will be analysed with Mann–Whitney U-tests. The Chi-squared or Fisher's exact test will be used to compare proportions and Pearson Product or Spearman Rank statistics will be used to assess correlation. Multiple regression exploratory analyses may be employed to estimate multiple effects simultaneously.

Data and all appropriate documentation will be stored for a minimum of 5 years after the completion of the study, including the follow-up period.

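### Recruitment runs at two hospitals, yet hospital is not a listed baseline field and has no stated place in allocation or analysis: a cheap, minor gain in precision is left unused

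*Combined protocol and SAP*

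**What the plan says.** - **Where patients come from.** Section 3.3 recruits from pre-operative orthopaedic clinics "within Imperial College Healthcare NHS Trust at St Mary's and Charing Cross Hospitals".
- **How the centre is defined.** Section 3.1 gives the study centre as "Imperial College Healthcare NHS Trust", and section 3.2 describes a "Single centre prospective randomised-controlled trial".
- **Baseline data.** Section 3.5 says "baseline demographic data will be collected on each participant, including age, gender, ethnicity and education level". The table in section 3.5.1 has the same four items ("Age, gender, ethnicity, education level"), as does section 5 ("These will include age, gender, ethnicity and educational level"). Health literacy is also measured before randomisation. Hospital appears in none of these places.
- **Allocation.** Section 6 says only that "Two hundred and six patients in total will be randomised using an online randomisation tool". It mentions neither stratification nor blocking.
- **Analysis.** Section 6 plans "comparisons between groups for normally distributed variables with independent samples t-test or ANOVA", Mann-Whitney tests for non-normal variables, and chi-squared or Fisher's exact tests for proportions. Multiple regression is optional and exploratory, and no covariates are named.

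**The concern.** The primary outcome is a service-satisfaction score. The CSQ-8 items in appendix 11.1 ask about the service in general terms, so a patient could rate the local clinic as well as the consent material. The choice of anaesthetic (appendix 11.3, question 16) concerns the patient's own operation, so it could vary with each clinic's mix of operations. The documents neither show nor exclude such differences.

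If they exist, a comparison that ignores hospital leaves the between-hospital variation in the error term. An allocation that ignores hospital also lets the arms differ by chance in hospital mix. At stake is some precision in comparing SVC minus VAC with the 1.5-point margin, and in comparing anaesthetic choice. The validity of the comparison is not at stake.

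**Working it through.** **Inputs from section 6:** 103 per arm, margin 1.5, SD 4, true means 30 in both arms, 5% level, stated power 85%. **Input from appendix 11.1:** eight items scored 1 to 4, so the total runs from 8 to 32. **Assumptions, because the documents give neither figure:** the hospital gap D in mean CSQ-8, and the share q of patients at one hospital.

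**1. The plan's own figure.** SE = 4 × √(2/103) = 0.557. A one-sided 5% t-test against 1.5 (noncentral t, 204 df) has 85.0% power, so the stated 85% reproduces. At one-sided 2.5% it would be 76.4%, so the plan's 5% is read as one-sided.

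**2. Gain from adjustment if SD 4 is the total SD.** The between-hospital variance is q(1−q)D². With q = 0.5:

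| D | Share of variance | Residual SD | Power, adjusted |
|---|---|---|---|
| 1 | 0.25/16 = 1.6% | √15.75 = 3.97 | 85.5% |
| 2 | 1.00/16 = 6.3% | √15.00 = 3.87 | 87.0% |

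With a 70:30 split the adjusted power is 85.4% and 86.7%.

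**3. The other reading: SD 4 is the within-hospital SD.** At 50:50 the total SD is then √16.25 = 4.03 or √17 = 4.12. The planned unadjusted test has 84.5% or 83.1% power, against 85.0% with adjustment.

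**4. Chance imbalance without stratification.** The 95% range for the difference between arms in hospital share is 1.96 × √(2 × 0.25/103) = ±13.7 percentage points (±12.5 at 70:30). With D = 2 this corresponds to 2 × 0.137 = 0.27 points on the arm difference.

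**5. Whether that 0.27 is an extra harm.** The unadjusted 95% half-width is 1.96 × 0.557 = 1.09 points. Its hospital component is √0.0625 × 1.09 = 0.27. This is the same variance as in step 2, seen from another side, and it must not be counted twice. Removing it narrows the half-width to √(1.09² − 0.27²) = 1.06.

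**6. How large a gap the scale allows.** At 50:50 with an overall mean of 30, the higher hospital has mean 30 + D/2. The largest possible SD at mean m on an 8–32 scale is √((32 − m)(m − 8)).
- D = 2: m = 31 and the maximum SD is √(1 × 23) = 4.80. The required 3.87 is possible but strained.
- D = 3: m = 31.5 and the maximum SD is √(0.5 × 23.5) = 3.43. The required residual SD is √(16 − 2.25) = 3.71, which cannot occur with equal within-hospital SDs.

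The limit in the D = 3 case belongs to the 50:50 split. At 70:30 with the larger hospital higher (means 30.9 and 27.9), the maximum SD is √(1.1 × 22.9) = 5.02. A 3-point gap is then not ruled out by arithmetic, and power would be 88.7%, but nothing in the documents suggests a gap of that size.

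**The case against.** The strongest reply is that nothing is broken. Individual randomisation makes the unadjusted test valid and unbiased on average. The documents contain no evidence that the clinics differ. Section 3.4 standardises the consent material as pre-recorded video in both arms, and the CSQ-8 wording is generic. All of this stands, and it is why the point is minor. Standardised material does not, however, standardise the clinic that a patient may have in mind when rating the service.

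A reader might infer more than the documents support:

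- **That the design description is contradictory.** It is not. Section 3.1 makes the Trust the centre and section 3.3 recruits within it, so one centre with two hospitals is consistent.
- **That hospital will not be recorded, so an imbalance could never be seen or corrected.** Sections 3.5 and 5 use open-ended wording. Hospital is unlisted, not excluded.
- **That the plan specifies a single unstratified draw of 206.** Section 6 does not mention stratification. That silence does not establish how many lists there will be.
- **That chance imbalance adds a bias of 0.27 points, or 18% of the margin.** Step 5 shows that this lies inside the usual confidence interval.

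It is also fair to say that the change is more than adding one term. Section 6 names simple tests, so a model would replace them. Separate blocked lists also need concealment and varying block sizes, or staff who can see the arms may guess the next allocation.

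**Conclusion.** The point holds as a cheap, minor improvement. Two hospitals recruit, and the plan states no role for hospital in baseline data, allocation or analysis. Under the assumed 50:50 split and a total SD of 4, adjustment is worth about half a percentage point of power for a 1-point gap and about 2 points for a 2-point gap. If 4 is the within-hospital SD, the same adjustment avoids a loss of about 0.5 or 1.9 points. If the hospitals do not differ, there is essentially no gain.

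The gap and the split are assumptions throughout. Treating gaps above 2 points as not credible is a judgement based on the ceiling at 32; arithmetic excludes the 3-point case only for an equal split with equal SDs. No bias and no invalid test is shown.

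**What to change.** 1. Add hospital to the fields recorded before randomisation. This also lets the feasibility analysis after 50 participants look at accrual and evaluability by clinic.
2. Use a separate, concealed 1:1 list for each hospital, with varying block sizes.
3. Prespecify the CSQ-8 comparison as a linear model with arm and hospital, and compare the confidence limit for SVC minus VAC with 1.5. Compare anaesthetic choice with hospital as a stratum, for example by a Mantel-Haenszel analysis.
4. If randomisation has already begun, do only the recording and the prespecified adjustment, and settle the adjustment before outcomes are examined by arm.

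The cost is one data field, a second allocation list, and a simple model and stratified test in place of the t-test and chi-squared test. The sample size and the single-centre description can stay as they are.

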3.4. PROTOCOL

Recruited participants will be randomised into two groups. The control group will undergo the standard video verbal consent process for both GA and RA for orthopaedic surgery. This will be delivered using a standardised video script that will be generated from existing certified material, as well as being reviewed by an experienced body of anaesthetists, in order to ensure that the length and content of information given is appropriate, unbiased, accurate and consistent. In order to account for adaptations to services in light of the coronavirus pandemic, and to further ensure standardisation, this verbal communication will be pre-recorded and shown to the participant. The intervention group will also be shown the same pre-recorded standard verbal consent, but following this will additionally be shown a specifically recorded video of the anaesthetic process for both GA and RA. This video will aim to communicate the same information as that found in the traditional verbal consent, using an actor undergoing an anaesthetic to provide context.

Following the consent process, participants from both groups will be asked to complete two questionnaires to enable assessment of participant satisfaction, retained knowledge and perceptions regarding anaesthesia from the consent process, and a stated preference for anaesthetic technique (i.e. GA or RA).

3.5. MEASUREMENTS

Following recruitment, baseline demographic data will be collected on each participant, including age, gender, ethnicity and education level.

Health literacy is the degree to which individuals have the capacity to obtain, process, and understand basic health information and services needed to make appropriate health decisions²⁸. Health literacy may be an important confounding factor within this study; therefore, assessing health literacy will be a useful screening tool prior to conducting the study. Prior to randomisation, participants will be asked to complete the Newest Vital Sign-UK questionnaire (*see appendix 11.2*) to assess health literacy.

For measuring the primary outcome, participant satisfaction, the Client Satisfaction Questionnaire (CSQ-8) will be utilised, which measures the most salient items for the satisfaction with services (*see appendix 11.1*). This will be administered for the control group after receiving standard verbal consent, and the intervention group after receiving video assisted consent.

For measuring the secondary outcomes, a knowledge, attitudes and practices (KAP) questionnaire will be utilised (*see appendix 11.3*). As part of the questionnaire, the participant will be offered the choice of anaesthetic technique between GA and RA. This is to evaluate whether the proportions choosing GA or RA differ between control and intervention groups.

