11.2. HEALTH LITERACY ASSESSMENT

Health literacy is defined as ‘the cognitive and social skills that determine the motivation and ability of individuals to gain access to, understand and use information in ways that promote and maintain good health’²⁸.

Health literacy may be an important confounding factor within this study. The Newest Vital Sign (NVS)-UK is a simple, accurate and validated predictor of health literacy skills that has been shown to take on average 3 minutes to complete, and can be administered by both clinical and non-clinical personnel³⁰.

NVS consists of a food nutrition label with six associated questions giving scores from 0 to 6

Product Description: Ice Cream	
Serving Size:	100ml
Servings per container:	4
NUTRITIONAL INFORMATION	
TYPICAL VALUES	Per 100ml
Energy	1050 kJ 250 kcal (calories)
Protein	4 g
Carbohydrate	30 g
of which sugars	23 g
Fat	13 g
of which saturates	9 g
of which monounsaturates	0 g
of which polyunsaturates	3 g
of which trans fats	1 g
Fibre	0 g
Sodium	0.05 g
Ingredients: Cream, Skimmed Milk, Sugar, Whole Egg, Stabilisers (Guar Gum), Peanut Oil, Vanilla Extract (0.05%).	

Question	Correct response
1. How many calories (kcal) will you eat if you eat the whole container?	1,000 KCAL or 1,000 CALORIES
2. If you are advised to eat no more than 60 grams of carbohydrate for dessert, what is the maximum amount of ice cream you could have?	Two servings (or anything up to 2 servings) OR Half the container (or any amount up to half the container) OR 200 ml (or any amount up to 200 ml).
3. Imagine that your doctor advises you to reduce the amount of saturated fat in your diet. You usually have 42 g of saturated fat each day, some of which comes from one serving of ice cream. If you stop eating ice cream, how many grams of saturated fat would you be eating each day?	33 g
4. If you usually eat 2500 calories each day, what percentage of your daily calorie (kcal) intake will you get if you eat one serving of ice cream?	1/10 (one tenth) OR 10%
Imagine that you are allergic to the following substances: penicillin, peanuts, latex gloves, and bee stings.	
5. Is it safe for you to eat this ice cream?	No
If 'No' to Q5:	
6. Why not?	Because it contains peanut oil/peanuts/nuts OR Because you might have an allergic reaction
ASK IF answer to Q6 is 'Because you might have an allergic reaction':	
7. Why would you have an allergic reaction?	Because it contains peanut oil/peanuts/nuts

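### Health literacy is scored in every participant before randomisation, but no eligibility rule or pre-specified analysis uses the score (an optional improvement, not an error)

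*Combined protocol and SAP*

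**What the plan says.** - **Reason for measuring it.** Section 3.5 states: "Health literacy may be an important confounding factor within this study". The same sentence continues that "assessing health literacy will be a useful screening tool prior to conducting the study". Appendix 11.2 repeats the confounding rationale.
- **When and in whom.** "Prior to randomisation, participants will be asked to complete the Newest Vital Sign-UK questionnaire". The table in Section 3.5.1 lists this step with the collection of age, gender, ethnicity and education level, and allows 3-5 minutes for it.
- **Scale.** "NVS consists of a food nutrition label with six associated questions giving scores from 0 to 6" (Appendix 11.2). No cut-off is given.
- **Eligibility.** Neither the Study Summary nor Section 3.1 has an NVS criterion. The nearest exclusion concerns language: "Inability to communicate in English or language difficulty that requires an interpreter".
- **Randomisation.** Section 6 names an online tool and mentions no stratification.
- **Analysis.** "It is planned to make comparisons between groups for normally distributed variables with independent samples t-test or ANOVA", with Mann-Whitney tests for variables that are not normally distributed. The only multivariable analysis is described thus: "Multiple regression exploratory analyses may be employed to estimate multiple effects simultaneously". Correlation statistics are also planned, with no variables named. NVS does not appear in Section 6.

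**The concern.** The protocol singles out one baseline variable as potentially important and measures it in everyone, then gives it no operational role. A screening tool implies selection, yet there is no threshold. A confounder implies adjustment or stratification, yet neither is planned.

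In a randomised trial, baseline literacy is a prognostic covariate rather than a systematic confounder, so leaving it out does not bias the comparison. Three smaller things are at stake:

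- a confidence interval for the CSQ-8 difference that may be wider than it need be;
- no correction if the arms happen to differ in literacy;
- an open choice of covariates after the results are seen, because the regression is optional and unspecified.

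**Working it through.** **Inputs from Section 6:** 103 per arm, SD 4, margin 1.5, true difference 0, 5% level. Sidedness is not stated. The correlation of NVS, age or education with CSQ-8 is not given anywhere, so every R² below is an assumption.

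**1. The plan's own figure.** SE = 4 × √(2/103) = 0.557, and the noncentrality is 1.5/0.557 = 2.69. With 204 degrees of freedom and a one-sided 5% test, the noncentral t distribution gives power of 85.0% (normal approximation 85.2%). The stated 85% is reproduced. At one-sided 2.5% the normal approximation gives 76.8%, so the plan must intend one-sided 5%. The distance from the estimate to the upper limit is 1.652 × 0.557 = 0.921.

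**2. Effect of adjustment.** With three covariate terms (NVS, age, education as an ordered score), the SE is multiplied by √(1 − R²). The variance is then multiplied by 1 + 3/200 = 1.015 to charge for estimating the terms, with 201 degrees of freedom. The equivalent unadjusted total is 206 / [(1 − R²) × 1.015].

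| Assumed R² | Power, no charge | Power, three terms charged | Estimate to upper limit | Equivalent total N |
|---|---|---|---|---|
| 0 | 85.0% | 84.5% | 0.928 | 203 |
| 5% | 86.6% | 86.1% | 0.904 | 214 (8 more) |
| 10% | 88.1% | 87.7% | 0.880 | 226 (20 more) |
| 20% | 91.2% | 90.9% | 0.830 | 254 (48 more) |

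Break-even is R² = 1 − 1/1.015 = 1.5%.

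**3. Ceiling.** CSQ-8 has eight items scored 1 to 4, so it runs from 8 to 32, and Section 6 expects a mean of 30. As an illustration, take a normal variable, round it, clip it to 8-32, and tune it so that the observed mean is 30 and the SD 4. About 69% of scores then sit at 32. Underlying correlations of 0.2 and 0.4 leave an observed R² of 2.3% and 9.3%, and power with three terms charged is 85.3% and 87.5%.

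**4. Error rate under the ceiling model** (20,000 simulated trials per setting; Monte Carlo SE √(0.05 × 0.95/20,000) = 0.15 percentage points). At a true difference of 1.5, with underlying correlations of 0, 0.2 and 0.4, type I error was 5.3%, 5.2% and 5.1% unadjusted, and 5.3%, 5.2% and 5.5% adjusted. A separate run of the last setting gave 5.1% for both analyses, so the 5.5% was not reproduced.

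**5. Chance imbalance.** The 95% limit for a difference in mean NVS between arms is 1.96 × √(2/103) = 0.27 SD. Unadjusted, it moves the CSQ-8 difference by r × 4 × 0.273. That is 0.11 points at r = 0.1, 0.33 at r = 0.3 and 0.55 at r = 0.5, against a margin of 1.5.

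**The case against.** The strongest case is that nothing is broken. The unadjusted comparison is valid, the sample size is met, and choosing an adjusted over an unadjusted primary analysis is largely a design preference. The benefit is also unproven. Under the ceiling model, an underlying correlation of 0.2 adds only 0.3 percentage points of power, and one of 0.4 gives an R² of 9.3%, so the 48-participant equivalent at R² = 20% is optimistic. All of that stands, and it is why this is no more than an optional improvement.

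Four further points:

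- **A purpose is stated, and exploratory regression could use the score.** True. What is missing is a rule or a named analysis. An optional regression with no covariates listed does not supply one.
- **Literacy bears more directly on knowledge than on satisfaction.** Reasonable, but it does not remove the possible gain for the primary endpoint.
- **The remedy needs details the protocol lacks.** This stands. Education categories are not listed, and dropping participants with a missing covariate would conflict with the intention-to-treat analysis. Both can be settled in a sentence each.
- **Adjustment might inflate type I error.** The one simulated value of 5.5% was not repeated in a separate run, so it is not a reason against adjustment.

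**Conclusion.** The point holds as an optional improvement. NVS-UK is collected from everyone before randomisation on the ground that it may matter, and neither the eligibility criteria nor any pre-specified analysis uses it. The planned comparison remains valid and reaches its stated 85% power, provided the test is one-sided at 5%.

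The likely gain runs from a fraction of a percentage point to a few points of power. About 6 points (90.9%) would require the covariates to explain 20% of CSQ-8 variance, which the ceiling makes doubtful. The worst case is a loss of about 0.5 points. These figures rest on assumed R² values and the plan's SD of 4. The mismatch between calling NVS-UK a screening tool and having no screening rule does not depend on any of these assumptions.

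**What to change.** **Section 6.** Make the primary estimate the SVC-VAC difference in CSQ-8 from one pre-specified linear model with arm, NVS score (0-6), age, and education level as an ordered score. Compare its upper one-sided 95% confidence limit with the existing 1.5-point margin. For this endpoint the model replaces the choice between t-test and Mann-Whitney; a Mann-Whitney test does not in any case estimate a mean difference that can be set against 1.5. List the education categories, and state how a missing baseline value will be handled so that no randomised participant with a CSQ-8 score is dropped. Report the unadjusted difference as a sensitivity analysis. Leave gender and ethnicity to the exploratory regression, so that the primary model keeps three covariate terms.

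**Section 3.5.** Replace the description of NVS-UK as a screening tool with this use of the score. If screening is intended, state the rule there and in Section 3.1.

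**Cost.** Changes of wording in Sections 3.5 and 6, and in 3.1 only if a screening rule exists. The model should be fixed before outcomes are compared by arm. No new data, participants or questionnaire changes are needed, and about 0.5 percentage points of power are at risk if the covariates prove uninformative.
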